4.3.3 Clinical Laboratory, Blood Sample

4.3.3.1 Definitions and Derivations

A full list of parameters (including other electrolytes) is provided in Appendix C: Laboratory Safety Variables.

These will be evaluated fasting at OLP Day 1, End of OLP and EOS for subjects not entering the RTP and at RTP Randomization visit, Visit 10, Visit 14 and EOS for those entering the RTP.

The date, time of collection and results (values, units and reference ranges) will be recorded in the appropriate eCRF module.

The clinical chemistry and hematology will be performed at a central laboratory.

Elevated liver test results

- ALT >3x, >5x, and >10x ULN during the study.
- AST >3x, >5x, and >10x ULN during the study.
- Total bilirubin $\geq 2x$ ULN during the study.

Hypokalemia

Hypokalemia is determined as potassium values <3.5 mmol/L.

4.3.3.2 Presentations

Descriptive statistics by time of assessment will be presented for each laboratory parameter including other serum electrolytes separately for OLP and RTP. All laboratory values will be classified as low, normal, or high based on normal ranges supplied by the central laboratory. For purposes of analyses, laboratory results based upon standardized units will be used.

For each summary of continuous variables, the number of non-missing observations, mean, median, standard deviation, minimum, and maximum values will be presented by study phase and treatment group for OLP and RTP.

Absolute values and change from baseline for all continuous haematology and clinical chemistry parameters will be summarized for OLP and RTP by treatment arm and scheduled visit.

Box plots of absolute values by scheduled visit, and box plots of change from baseline by visit, may be presented for certain parameters if warranted after data review.

Any treatment-emergent laboratory data reported as abnormal according to reference values as well as individuals with treatment-emergent, abnormal serum laboratory values will be summarized and listed for the relevant safety analysis set by treatment group presented separately for the OLP and the RTP.

Additionally, subject listings and summary of all on-treatment hematology and chemistry changes will be provided for OLP and RTP by treatment group.

Elevated liver test results

Maximum on-treatment ALT and AST versus maximum total bilirubin will be presented. Listings of liver biochemistry test results will be provided, separately for OLP and RTP.

Hypokalemia

Tabulation of the number and percentage of subjects with hypokalemia (<2.5 mmol/L, <3 mmol/L, <3.5 mmol/L) at any point during a phase (OLP and RTP), while on treatment, will be presented by treatment group.

4.3.4 Clinical Laboratory, Urinalysis

4.3.4.1 Definitions and Derivations

A full list of the urinalysis parameters for this study (including other electrolytes) is provided in Appendix C: Laboratory Safety Variables

These will be evaluated fasting at OLP Day 1, End of OLP and EOS for subjects not entering the RTP and at RTP Randomization visit, Visit 10, Visit 14 and EOS for those entering the RTP.

The date, time of collection and results (values, units and reference ranges) will be recorded in the appropriate eCRF module.

The urinalysis will be performed at a central laboratory.

4.3.4.2 Presentations

Absolute values and change from baseline for all continuous urinalysis will be summarized for OLP and RTP by treatment arm and visit.

Urinalysis baseline versus maximum value on treatment shift table will be provided for categorical urinalysis parameters.

If applicable, urinalysis values will be classified as low, normal, or high based on normal ranges supplied by the central laboratory and presented in a shift table as described above. For purposes of analyses and where applicable, urinalysis results based upon standardized units will be used.

4.3.5 Other Laboratory Evaluations

4.3.5.1 **Definitions and Derivations**

In addition to the urinalysis urine-HCG will also be collected during the study. The OLP Day 1 urine pregnancy test for women of childbearing potential is performed as part of the screening procedure prior to any IP administration and is repeated at the last visit of the study, either on the OLP EOS visit, or on the RTP EOS visit.

4.3.5.2 Presentations

These data will be listed only, no summary tables will be produced.

4.3.6 Vital Signs

4.3.6.1 **Definitions and Derivations**

Pulse rate and systolic and diastolic blood pressure (BP) will be assessed at OLP Day 1, End of OLP and EOS for subjects not entering the RTP and at RTP Randomization visit, Visit 10, Visit 14 and EOS for those entering the RTP.

4.3.6.2 Presentations

Summary statistics for vital signs will be calculated for absolute values and change from baseline to each subsequent planned visit where applicable. For each summary, the number of non-missing observations, mean, median, standard deviation, minimum, and maximum will be presented by treatment group for each study phase (OLP and RTP).

Baseline versus maximum value on treatment shift table will be provided for all vital sign parameters.

Any treatment-emergent, abnormal vital signs will be summarized and listed for the safety analysis set by treatment group for each study phase (OLP and RTP).

4.3.7 Physical examinations

4.3.7.1 Definitions and Derivations

Any new or aggravated clinically relevant abnormal medical findings at a physical examination as compared with the baseline assessment will be reported as an AE.

4.3.7.2 Presentations

No separate analyses for Physical Examinations will be provided.

4.3.8 Electrocardiogram

4.3.8.1 **Definitions and Derivations**

ECG mean heart rate, P wave duration and QRS durations, PR and QTc intervals aggregate will be recorded at OLP Day 1, Day 2, End of OLP and EOS for subjects not entering the RTP, and at RTP Randomization Visit (RTP Day 1), Visits 5, 8, 10, 12, 14, and EOS for those entering the RTP.

QTc intervals

QTc intervals will be calculated using the Fridericia formula:

$$QTcF = \frac{QT(msec)}{(RR(msec)/1000)^{1/3}}$$

Where:

- 1. RR(msec) = (60/HR) * 1000
- 2. RR = RR interval
- 3. HR = Heart rate.

4.3.8.2 Presentations

Overall ECG evaluations will be presented in a shift table showing baseline classification against last on-treatment (OLP and RTP) classification, by treatment group.

The following ECG variables will be descriptively summarized by treatment group and visit to include change from baseline to each subsequent visit: ECG mean heart rate, P wave duration, PR interval aggregate, QRS duration aggregate, QT interval aggregate and QTcF interval aggregate. The summaries will be presented for OLP and RTP, separately.

A listing of subjects with overall ECG evaluation reported as abnormal or borderline abnormal will also be provided.

QTc intervals

Number and percentage of subjects for QTcF for the following categories will be provided for OLP and RTP, by treatment group.

• QTcF value above 450 ms at baseline (>450 ms, 480 ms and > 500 ms):

- QTcF value above 450 ms at any time during treatment (>450 ms, 480 ms and > 500 ms):
- QTcF increase by more than 30 ms at any time during treatment (>30 ms, >60 ms and >90 ms)
- QTcF value above 450 ms and QTcF increase [a] by more than 30 ms at any time during treatment [(value > 450 ms and increase >30 ms and (value > 500 ms and increase >60 ms)]
- QTcF decrease by more than 30 ms at any time during treatment (>30 ms, >60 ms and >90 ms).

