3.9 Discontinuation of investigational product

Patients may be discontinued from investigational product (IP) in the following situations:

- Patient decision. The patient is at any time free to discontinue treatment, without prejudice to further treatment.
- Adverse Event

Clinical Study Protocol Drug Substance ZS Study Code **D9480C00001** Version **6.0** Date **19** August 2020

- Severe non-compliance with the study protocol
- Risk to patient as judged by investigator
- Pregnancy
- Require treatment with medications prohibited or contraindicated for use due to safety concerns with ZS
- Start dialysis while in the study
- Patient unblinded due to emergency
- Patients who change or switch RAAS inhibitor and/or diuretic dose during the study
- Patient develops severe hypokalemia (i-STAT potassium values <3.0 mmol/L) at any time during the study or has i-STAT level > 6.2 mmol/L during the 28-day randomized treatment study phase (confirmed by taking a second potassium measurement after a 10 ± 2-minute interval, and both i-STAT values meet the study drug discontinuation rule). Patients discontinuing due to this criterion must immediately receive appropriate medical treatment to manage their hypo- or hyperkalemia.
- Patient has a clinically significant cardiac arrhythmia (see below) at any time in the 28day randomized treatment study phase, the patient should immediately receive appropriate medical treatment and be discontinued from study drug. Any of the following cardiac events will result in immediate discontinuation from the study drug (independent of whether it is in the open-label initial phase or the 28-day randomized treatment study phase):
 - Serious cardiac arrhythmias (ventricular tachycardia or ventricular fibrillation, new atrial fibrillation or atrial flutter, new paroxysmal supraventricular tachycardia [other than sinus tachycardia], new 2nd or 3rd degree AV block or significant bradycardia [HR < 40 bpm])
 - Acute heart failure
 - Significant increase in PR interval (> 250 msec in the absence of pre-existing atrioventricular block), widening of the QRS complex (>140 msec in the absence of pre-existing bundle branch block) or new onset peaked T-wave

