5.2.3 ECG

A 12-lead ECG will be performed after the patients has been lying down for 5 minutes at the times indicated in the Study Plan in Table 1 and Table 2. Heart rate, P and QRS durations, PR and QTc(f) intervals will be recorded from standard lead of the computerized quantitative 12-lead ECG.

ECGs will be recorded at the open-label initial phase Day 1, Day 2, the open-label initial phase Day 3 and Day 9 (EOS) for patients NOT entering the double-blind 28-day randomized

treatment study phase, and on the 28-day randomized treatment study phase Days 1, 8, 15, 22, 29, and 35 (EOS). When applicable ECGs will be performed after the S-Aldo and P-Renin samples are drawn and before the first daily dose of IP.

In addition, for patients who have i-STAT potassium levels $\geq 6.1 \text{ mmol/L}$ or $< 4.0 \text{ but } \geq 3.5 \text{ mmol/L}$ at the 4 hour post 1st dose time point on the open-label initial phase Day 1, an additional ECG will be recorded 1.5 hours post 2nd dose. Patient who develops severe hypokalemia (i-STAT potassium values <3.0 mmol/L) at any time during the study or > 6.2 mmol/L during the 28-day randomized treatment study phase, an additional ECG will need to be performed.

Study subjects with pacemakers:

All ECG variables, including QT/QTc(f), should be read manually and be recorded in the eCRF. If not fulfilling the I/E criteria or fulfilling the discontinuation criteria, pacemaker patients should be managed as recommended by protocol (without exceptions).

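### The only by-arm table of overall ECG evaluation uses the last on-treatment ECG, so abnormalities that clear by Day 29 are not counted in it

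*SAP*

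**What the plan says.** SAP 4.3.8.2 plans four kinds of ECG output.

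- **Overall evaluation, by arm:** "Overall ECG evaluations will be presented in a shift table showing baseline classification against last on-treatment (OLP and RTP) classification, by treatment group".
- **Continuous parameters, by arm and visit:** "The following ECG variables will be descriptively summarized by treatment group and visit to include change from baseline to each subsequent visit". These are heart rate, P wave, PR, QRS, QT and QTcF.
- **Overall evaluation, listing only:** "A listing of subjects with overall ECG evaluation reported as abnormal or borderline abnormal will also be provided".
- **QTcF categories, by arm:** mostly any-time counts, such as "QTcF value above 450 ms at any time during treatment", together with categories of increase and decrease.

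Elsewhere the SAP builds its shift tables on the extreme value. For vital signs (SAP 4.3.6.2): "Baseline versus maximum value on treatment shift table will be provided for all vital sign parameters". SAP 4.3.4.2 does the same for categorical urinalysis. Treatment-emergent abnormal laboratory values and vital signs are also summarized by arm (SAP 4.3.3.2 and 4.3.6.2). The overall ECG evaluation has neither treatment.

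**The concern.** An ECG abnormality driven by potassium can come and go. Some patients with low potassium have their dosing frequency reduced and stay on treatment (Protocol 7.2), so their later ECGs follow the change. A table that keeps only the last ECG can show such a patient as normal even if an earlier on-treatment ECG was not.

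What is at stake is a by-arm count of patients with any abnormal overall evaluation while on treatment. It matters most for categorical findings such as T-wave or rhythm changes, which neither the interval summaries nor the QTcF counts can show. New peaked T waves are among the stopping criteria in Protocol 3.9, beside "Significant increase in PR interval (> 250 msec in the absence of pre-existing atrioventricular block), widening of the QRS complex". No efficacy result is affected.

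**Working it through.** The plan states no figure here to reproduce. The check is a reading of the two documents, followed by an illustration.

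**Step 1. Is there another by-arm count of the overall evaluation?** Of the four outputs, the by-visit summaries cover continuous parameters, the any-time counts cover QTcF, and the listing has no counts by arm. Only the shift table tabulates the overall evaluation by arm.

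**Step 2. Which ECG is the last on-treatment one?**

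- Schedule: Protocol 5.2.3 places randomized-phase ECGs on Days 1, 8, 15, 22, 29 and 35. SAP 4.3.8.1 gives "Visits 5, 8, 10, 12, 14, and EOS for those entering the RTP"; by SAP Table 2, Visits 8, 10, 12 and 14 are Days 8, 15, 22 and 29.
- Window: SAP 3.3.1.2 ends the randomized on-treatment period one day after the last dose.
- Last dose: Day 28 (Protocol Table 2, footnote 7, and Protocol 4.3.13).
- Result: 28 + 1 = 29. Day 29 is inside the window and Day 35 is outside. Of four scheduled post-baseline on-treatment ECGs, the shift table uses one. An abnormal Day 8, 15 or 22 evaluation followed by a normal Day 29 is counted as normal.
- Exceptions: a patient who stops early has an earlier last on-treatment ECG. If the final visit falls more than one day after the last dose, Day 22 can become the last.

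**Step 3. Does another rule rescue it?** SAP 3.3.3 brings in all post-baseline values, unscheduled ones included, but only for summaries of minimum or maximum values. A last-value table is not one of these. Under SAP 3.3.4, unscheduled visits get no separate row in summary tables. In the open-label phase, the extra ECG after the second dose on Day 1 for flagged patients (Protocol 4.3.1 and 5.2.3) would normally be superseded by the ECG of the next visit.

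**Step 4. How large could the gap be?** The documents give no rate of abnormal evaluations. Assume that a new abnormality occurs independently with probability p at each of the four ECGs and does not carry over. Then

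P(at least one) = 1 − (1 − p)^4, while the last-value table shows p.

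| Assumed p | At least one | Last-value table | Not shown, arm of 100 | Not shown, arm of 50 |
|---|---|---|---|---|
| 2% | 1 − 0.98^4 = 7.8% | 2% | 5.8 | 2.9 |
| 5% | 1 − 0.95^4 = 18.5% | 5% | 13.5 | 6.8 |
| 10% | 1 − 0.90^4 = 34.4% | 10% | 24.4 | 12.2 |

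Arm sizes are those of Protocol 8.2, taking every patient to Day 29. This is the fully transient extreme. If every abnormality lasts to Day 29, the two columns agree and the gap is zero.

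**The case against.** The strongest reply is that the ECG data are well covered without this table.

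- PR and QRS are summarized by arm at every visit, and SAP section 4 includes minimum and maximum among the descriptive statistics. The longest PR and QRS at each visit in each arm will therefore be displayed.
- QTcF has any-time counts by arm, and every abnormal or borderline evaluation is listed.
- ECG findings that meet the criteria in Protocol 3.9 lead to immediate discontinuation. Because the window closes one day after the last dose, the triggering ECG will often be the last on-treatment one and so be counted, while later recovery ECGs fall outside.
- Events reported as adverse events are tabulated by arm (SAP 4.3.2.2).
- Nothing in the SAP promises one shift-table rule for all domains, so the difference from vital signs is not a contradiction.
- The same rule applies in every arm, and no distortion between arms has been shown.
- A worst-category table would not say whether the finding was in PR, QRS or the T wave, and a last-value table has its own use as a record of status at the end of treatment.

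All of this stands, and it narrows the point to patients who continue dosing after an abnormal ECG. It does not supply the missing item: no planned output counts, by arm, the patients with any abnormal overall evaluation on treatment.

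**Conclusion.** The point holds as a small gap in reporting. For patients dosed to Day 28, the by-arm table of overall ECG evaluation rests on Day 29 and can understate transient abnormalities. The size is unknown. The gaps of 5.8, 13.5 and 24.4 patients per 100 depend on assumed rates and on independence between visits, and the true gap may be near zero.

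A reader might infer more, and the documents do not support it:

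- *Three of four ECGs are ignored.* That is so for this one table only. The by-visit summaries, the any-time QTcF counts and the listing use the others.
- *PR and QRS appear only in a listing.* They have by-arm, by-visit summaries. What they lack is a count of patients beyond a threshold.
- *The table will generally show recovery.* That is plausible for patients who stay on treatment. For those who stop because of an ECG finding it often works the other way.
- *ECG monitoring was increased in protocol version 3.0 to feed this comparison.* The version history gives alignment with a regulator's recommendation and closer patient monitoring as the reasons, not a tabulation by arm.

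**What to change.** In SAP 4.3.8.2, keep the last-value table and add beside it a by-arm shift table of baseline against worst on-treatment overall ECG evaluation, separately for the open-label and randomized phases. Order the categories normal, borderline abnormal, abnormal, and include unscheduled ECGs that fall in the on-treatment window. This brings the ECG output into line with the maximum-value shift tables for vital signs and urinalysis.

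The cost is one derivation rule and one extra table from data already collected. Study conduct, sample size and the efficacy analyses do not change. The new table will show more abnormal results in every arm, placebo included, so it should be read by comparing arms. The rule is best written in before unblinding; if added later, the table should be labelled as such.

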4.3.9 Other Safety Assessments

Not applicable.

7 APPENDIX

7.1 Appendix A: IPD Master List

IPD Code	IPD	CSP Version	Identification method	Source for
		and Date		identification
1	Inclusion Criteria Deviations - Subjects who were enrolled or	randomized but die	d not meet critical inclusion cri	iteria.
1.1	Provision of informed consent (pre-screening consent - as applicable) prior to any study specific procedures.	CSP v6.0 (19-Aug-2020)	EDC Automatic CheckManual CRA review	DM: CONSENT1, VISIT2
1.2	Male and female subjects aged 18 to 90 years, inclusive	CSP v6.0 (19-Aug-2020)	EDC Automatic CheckManual CRA review	DM
1.3	Provision of informed consent prior to any study specific procedures	CSP v6.0 (19-Aug-2020)	EDC Automatic CheckManual CRA review	DM: CONSENT, VISIT1
1.4	Two consecutive i-STAT potassium values, measured 60- minutes (\pm 10 minutes) apart, both \geq 5.1 mmol/L and measured within 1 day of the first ZS dose on open-label initial phase Day 1	CSP v6.0 (19-Aug-2020)	 EDC Automatic Check B&I Programming Source Data review 	DM: LB, EX
1.5	Ability to have repeated blood draws or effective venous catheterization	CSP v6.0 (19-Aug-2020)	- Source Data review	
1.6	Female patients must be 1 year post-menopausal, surgically sterile, or using an acceptable method of contraception (an acceptable method of contraception is defined as a barrier method in conjunction with a spermicide) for the duration of the study (from the time they sign consent) and for 3 months after the last dose of ZS/matching placebo to prevent pregnancy. In addition, oral contraceptives, approved contraceptive implant, long-term injectable contraception, intrauterine device, or tubal ligation are allowed. Oral contraception alone is not acceptable; additional barrier methods in conjunction with spermicide must be used	CSP v6.0 (19-Aug-2020)	- Source Data review	

STATISTICAL ANALYSIS PLAN

D9480C00001 - ed. 3.0

AstraZeneca 24-Oct-2022

1.7	Randomized to the 28-day randomized treatment study phase,	CSP v6.0	- EDC Automatic Check	DM: LB2
	even though not fulfilling randomization criteria: The i-STAT	(19-Aug-2020)	- B&I Programming	
	potassium value is within the normal range (3.5 to 5.0		- Source Data review	
	mmol/L, inclusive).			
	Refer to CSP sec. 4.3 for details about randomization criteria			
2	Exclusion Criteria Deviations - Subjects who were enrolled or	r randomized even	though they fulfilled the critica	l exclusion criteria.
2.1	Participation in another clinical study with an investigational	CSP v6.0	- Source Data review	
	product during the last 3 months	(19-Aug-2020)		
2.2	Presence of any condition which, in the opinion of the	CSP v6.0	- Source Data review	
	investigator, places the patient at undue risk or potentially	(19-Aug-2020)		
	jeopardizes the quality of the data to be generated			
2.3	Pseudohyperkalemia signs and symptoms, such as hemolyzed	CSP v6.0	- Source Data review	
	blood specimen due to excessive fist clenching to make veins	(19-Aug-2020)		
	prominent, difficult or traumatic venepuncture, or history of			
	severe leukocytosis or thrombocytosis			
2.4	Patients treated with lactulose, xifaxan (rifaximin) or other	CSP v6.0	- B&I Programming	CM: EX
	non-absorbed antibiotics for hyperammonemia within 7 days	(19-Aug-2020)	- Source Data review	
	prior to the first dose of study drug			
2.5	Patients treated with resins (such as sevelamer acetate or	CSP v6.0	- B&I Programming	CM: EX
	sodium polystyrene sulfonate [SPS; e.g. Kayexalate®]),	(19-Aug-2020)	- Source Data review	
	calcium acetate, calcium carbonate, or lanthanum carbonate,			
	within / days prior to the first dose of study drug			
2.6	Patients with a life expectancy of less than 3 months	CSP v6.0	- Source Data review	
2.7		(19-Aug-2020)		
2.7	Patients who are severely physically or mentally incapacitated	CSP v6.0	- Source Data review	
	and who in the opinion of investigator are unable to perform	(19-Aug-2020)		
2.0	Equals action to subject tasks associated with the protocol	CCD = (0)		DM. DDEC.
2.8	Female patients who are pregnant, factating, or planning to	(10 Aug 2020)	- EDC Automatic Check	DMI: PREG: VISIT
	become pregnant	(19-Aug-2020)	- Source Data review	V1511
2.9	Patients with diabetic ketoacidosis	CSP v6.0	- B&I Programming	МН
,		(19-Aug-2020)	- Source Data review	17111
2.10	Known hypersensitivity or previous anaphylaxis to ZS or to	CSP v6 0	- Source Data review	
	components thereof	(19-Aug-2020)		
2.11	Patients with cardiac arrhythmias that require immediate	CSP v6.0	- Source Data review	

	treatment	(19-Aug-2020)		
2.12	History of QT prolongation associated with other medications	CSP v6.0	- Source Data review	
	that required discontinuation of that medication	(19-Aug-2020)	- B&I Programming	
2.13	Congenital long QT syndrome	CSP v6.0	- Source Data review	MH
		(19-Aug-2020)	- B&I Programming	
2.14	Symptomatic or uncontrolled atrial fibrillation despite	CSP v6.0		
	treatment, or asymptomatic sustained ventricular tachycardia.	(19-Aug-2020)	- Source Data review	
	Subjects with atrial fibrillation controlled by medication are			
	permitted			
2.15	QTc(f) > 550 msec	CSP v6.0	- EDC Automatic Check	DM:
		(19-Aug-2020)	- Source Data review	EG,EG1,EG2,EG
				3
2.16	Patients on dialysis	CSP v6.0	- Source Data review	
		(19-Aug-2020)		
3	Discontinuation Criteria for study product met but patient	not withdrawn fro	m study treatment	
3.1	Patient Decision to discontinue treatment but patient not	CSP v6.0	- EDC Automatic Check	DM: EX: EX1:
	withdrawn from study treatment	(19-Aug-2020)	- Source Data review	DOSDISC
3.2	Adverse Event requiring IP discontinuation but patient not	CSP v6.0	- EDC Automatic Check	DM: EX: EX1:
	withdrawn from study treatment	(19-Aug-2020)	- Source Data review	DOSDISC
3.3	Severe non-compliance with the study protocol (as assessed	CSP v6.0	- Source Data review	
	by Investigator and/or AZ)	(19-Aug-2020)		
3.4	Patient not discontinued from study medication although Risk	CSP v6.0	- Source Data review	
	to subjects was judged by the investigator	(19-Aug-2020)		
3.5	Pregnancy is confirmed	CSP v6.0	- EDC Automatic Check	DM: PREG:
		(19-Aug-2020)	- Source Data review	DOSDISC
36	Require treatment with medications prohibited or	CSP v6 0	- Source Data review	
5.0	contraindicated for use due to safety concerns with 7S	$(19-\Delta 110-2020)$	- Source Data review	
37	Start dialysis while in the study	$\frac{(1)^{-1}(\log^2 2020)}{(SP v6.0)}$	- Source Data review	
0.7	Start diarysis while in the study	(19-Aug-2020)	Source Data Teview	
3.8	Patient unblinded due to emergency	CSP v6 0	- Source Data review	
		$(19-A_{11}g-2020)$	Source Data Torrew	
3.9	Patients who change or switch RAAS inhibitor and/or diuretic	CSP v6 0	- Source Data review	
	dose during the study	(19-Aug-2020)	Source Dute review	
3.10	Patient develops severe hypokalaemia (i-STAT notassium	CSP v6 0	- EDC Automatic Check	DM·
	r anone acteropo setere nypokalacinia (r o ritri potassiani			2.01.

	values <3	3.0 mmol/L) at any time during the study or has i-	(19-Aug-2020)	- Source Data review	LB,LB1,LB2,LB
	STAT le	vel $> 6.2 \text{ mmol/L}$ during the 28-day randomized			3: EX: EX1:
	treatment	t study phase (confirmed by taking a second			DOSDISC
	potassiur	n			
	measurer	nent after a 10 ± 2 -minute interval, and both i-STAT			
	values m	eet the study drug discontinuation rule).			
	Patient h	as a clinically significant cardiac arrhythmia (see			
	below) at	t any time in the 28-day randomized treatment study			
	phase, th	e patient should immediately receive appropriate			
	medical t	treatment and be discontinued from study drug. Any			
	of the fol	lowing cardiac events will result in immediate			
	discontin	uation from the study drug (independent of whether			
	it is in th	e open-label initial phase or the 28-day randomized			
	treatment	t study phase):			
	3.11.1	- Serious cardiac arrhythmias (ventricular		- EDC Automatic Check	DM:
		tachycardia or ventricular fibrillation, new atrial		- Source Data review	AE:DOSIDISC
		fibrillation or atrial flutter, new paroxysmal			
		supraventricular tachycardia [other than sinus	CSD v6 0		
		tachycardia], new 2nd or 3rd degree AV block or	(10 Aug 2020)		
		significant bradycardia [$HR < 40$ bpm])	(19-Aug-2020)		
3.11	3.11.2	- Acute heart failure		- B&I Programming -	DM: EG2, EG3:
				Source Data review	DOSDISC
	3.11.3	- Significant increase in PR interval (> 250 msec		- EDC Automatic Check -	DM: EG,
		in the absence of pre-existing atrioventricular		Source Data review	EG2,EG3:
		block), widening of the QRS complex (>140 msec			DOSDISC
		in the absence of pre-existing bundle branch block)			
		or new onset peaked T-wave.			
	3.11.4	- An absolute $QTc > 550msec$, or an increase in		- EDC Automatic Check	DM: AE:
		QTc interval > 60msec from baseline to more than		for QTcF only	DOSDISC
		500msec. All patients meeting the QTc>500ms		- B&I Programming -	
		criterion should immediately have potassium		Source Data review	
		assessed by i-STAT and central lab, if not already			
		done within 1 hour of the collection of the ECG.			
		The QTc(f) algorithm (QT interval corrected by the			

	Fridericia method) is recommended.			
4	Discontinuation Criteria for overall study withdrawal met b	out patient not wit	hdrawn from study	
4.1	Voluntary discontinuation by the patient	CSP v6.0 (19-Aug-2020)	- Source Data review	
4.2	Severe non-compliance to protocol as judged by the Investigator and/or Sponsor	CSP v6.0 (19-Aug-2020)	- Source Data review	
5	Investigational Product (IP) Deviation			
5.1	Participant received incorrect IP (corporate IPD):Subject received incorrect IP to that to which they were randomised.	CSP v6.0 (19-Aug-2020)	- Source Data review	
5.2	Subjects who were randomised but did not receive IP	CSP v6.0 (19-Aug-2020)	- B&I Programming - Source Data review	DS: DS1: IE1; EX1: DOSDISC
5.3	Incorrect Dose Adjustment during Open Label Phase: If a patient develops confirmed i-STAT potassium values between 3.0 mmol/L and 3.4 mmol/L, inclusive, during the open-label initial phase, but patient takes more ZS during the rest of that day. (refer to CSP sec. 7.2)	CSP v6.0 (19-Aug-2020)	- B&I Programming - Source Data review	LB: LB1: EX
5.4	Incorrect dose adjustment during 28-Day Randomized Treatment Phase: If a patient develops i-STAT potassium values between 3.0 mmol/L and 3.4 mmol/L, inclusive (confirmed by taking a second potassium measurement after a 10 ± 2 minute interval), during the 28 -day randomized treatment study phase, dosing is not reduced from qd to qod for the remainder of the study.	CSP v6.0 (19-Aug-2020)	- Source Data review	-
5.5	Incorrect dose adjustment during 28-Day Randomized Treatment Phase: After dosing reduced from qd to qod, if a patient i-STAT potassium value is back to normal (3.5 – 6.2 mmol/L inclusive), during the 28-day randomized treatment study phase, dosing is increased back from qod to qd for the remainder of the study.	CSP v6.0 (19-Aug-2020)	- Source Data review	
5.6	Use of expired IP	CSP v6.0 (19-Aug-2020)	- Source Data review	
6	Excluded Medications taken			

STATISTICAL ANALYSIS PLAN

6.1	Subject received concomitant medication defined as	CSP v6.0	- Manual Physician Review	СМ
	prohibited in the CSP (corporate IPD).	(19-Aug-2020)	based on CMR/GPR reports	
	Administration of prohibited concomitant medication or non-		- B&I Programming	
	drug therapy as outlined in CSP sec 7.7)		- Source Data Review	
7.	Deviations to study procedure			
7.1	Two or more successive visits missed or not performed	CSP v6.0	- B&I Programming	VISIT, VISIT1
	according to the protocol	(19-Aug-2020)	- Source Data Review	
7.2	Any of the following visits missed:	CSP v6.0	- B&I Programming	VISIT, VISIT1
	For those patients randomized (with patient randomization	(19-Aug-2020)	- Source Data Review	
	number) on Day 2 and get randomized same day, they should			
	complete:			
	- Enrolment/screening visit			
	- Open label initial phase Day 1			
	- Randomization visit			
	For those patients randomized (with patient randomization			
	number) on Day 3 they should complete.			
	- Enrolment/screening visit			
	- Open label initial phase Day 1			
	- Open label initial phase Day 2			
	- Randomization visit			
	For those patients who failed OLP, they should complete:			
	- Enforment/screening visit			
	- Open label initial phase Day 1 Open label initial phase Day 2			
	- Open label initial phase Day 2			
73	Patient is not fasting for any of the following visits as per	CSP v6 0	EDC Automatic Check	DM· I B
7.3	nrotocol for K sample for i-STAT or central lab for open-label	$(19-\Delta 110-2020)$	for Local Labs only	L R1 L R2
	initial phase.	(1 ) - i ug-2020)	- Source Data Review	
	- Day 1 – Omin (1st potassium sample for assessment pre-		- Source Data Review	
	dose)			
	- Day $1 - 60 \min (2 \ln \theta \operatorname{potassium} \operatorname{sample} \operatorname{for} \operatorname{assessment} \operatorname{pre}$			
	dose)			
	- Day 2 or Day 3 or Randomization – 0 min (pre-dose)			

STATISTICAL ANALYSIS PLAN

7.4	Missing ALL of the following i-STAT and central lab	CSP v6.0	- EDC Automatic Check	DM: LB
	potassium samples (as applicable) for Open-label initial	(19-Aug-2020)	for Local Labs only	
	phase:		- Source Data Review	
	- Day 1 – 0min (1st potassium sample for assessment, pre-			
	dose)			
	- Day 1 – 60 min (2nd potassium sample for assessment, pre-			
	dose)			
7.5	Missing the i-STAT and central lab potassium samples for	CSP v6.0	- EDC Automatic Check	DM: LB1, LB2
	Randomization Visit (open-label initial phase Day 2 or Day 3)	(19-Aug-2020)	for Local Labs only	
	$-0 \min (\text{pre-dose})$		- Source Data Review	
7.6	Patient is not fasting for any of the following visits as per	CSP v6.0	- EDC Automatic Check	DM: LB2
	protocol for S-K sample for i-STAT or central lab for	(19-Aug-2020)	for Local Labs only	
	Randomized Treatment Phase – Day 1, 15, 29, 35		- Source Data Review	
7.7	For subjects randomized and not withdrawn before Day 8 of	CSP v6.0	- EDC Automatic Check	DM: LB2,
	the 28-day randomized treatment study phase, missing BOTH	(19-Aug-2020)	- B&I Programming	ASMPERF: DS1:
	the i-STAT and central lab potassium samples from Day 8 to		- Source Data review	DS: VISIT
	Day 28			
7.8	Missing any of two consecutive i-STAT potassium values,	CSP v6.0	- Source Data review	
	measured ± 10 minutes apart during study drug adjustment or	(19-Aug-2020)		
	patient discontinuation			
8	Other Important Protocol Deviations (including missing PI	eCRF signature [c	orporate IPD], others to be a	greed by Study
	Team)			
8.1	Any deviation considered important that was not predicted or	CSP v6.0	- Source Data review	
	prespecified.	(19-Aug-2020)		
8.2	Add study specific IPDs that are not covered by any category	CSP v6.0	- Source Data review	
	above.	(19-Aug-2020)		

Statistical Analysis Plan Study Code D9480C00001 Edition Number 1.0 Date

